### **PROJECT SUMMARY / ABSTRACT**

---

Premature ventricular contractions (PVCs) coexist in subjects with heart failure (HF) and LV dysfunction. Frequent PVCs have been shown to induce a reversible cardiomyopathy (PVC-CM). Yet, it is unclear why some subjects develop PVC-CM, while others do not. Retrospective and observational studies have shown improvement of LV function after PVC suppression via radiofrequency ablation (RFA). Thus, appropriate diagnosis and treatment of subjects with PVC-CM is believed to carry significant benefits, improving quality of life (QOL), HF symptoms / admissions and life expectancy. Currently, these subjects are offered RFA, antiarrhythmic drugs (AADs) or no treatment depending on physician's experience and resources. Thus, there is clear need for a large clinical trial comparing these treatment strategies. Yet, we need to better understand the prevalence of PVC-CM, feasibility and limitations of such a trial.

**Research Design and Methods.** We propose a clinical pilot study, enrolling between 36-39 subjects with frequent PVCs (burden  $\geq 10\%$ ) and CM (LVEF  $\leq 45\%$ ) and randomize them to either: 1) RFA or 2) AADs. Prior to treatment, a baseline cardiac MR will be requested if clinically indicated followed by a 3-month observation period. We plan to follow changes in LV function/scar, PVC burden/arrhythmias and clinical/functional status (QOL, HF symptoms and admissions, NYHA class) and adverse events throughout the observation period and compare with PVC suppression strategies (RFA or AAD). Similar comparison will be made between RFA and AAD treatment groups during a 12-month follow up using a Prospective Randomized Open, Blinded End-point (PROBE) study design. The treatment regimens will be compared in an intention-to-treat analysis.

In addition, we plan to screen 20,000 consecutive ambulatory ECG Holter monitors of all participating centers (1,500 per participating center) to identify all subjects with probable diagnosis of PVC-CM (PVC burden  $> 10\%$  and LVEF  $< 45\%$ ).

This pilot study is intended to estimate the prevalence of this clinical entity and pave the way for a large full scale randomized trial to identify the best treatment strategy for subjects with PVC-CM. Treating and reversing this underestimated PVC-CM may improve subject's health and subsequently decrease HF healthcare spending.

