**A. Study Population and Eligibility**

This is a prospective randomized pilot study including between 36-39 subjects with cardiomyopathy (CM) and high PVC burden with a likely diagnosis of PVC-CM, where all subjects will be assigned to a 1:1 random allocation to one of two un-blinded PVC suppression groups: 1) PVC radiofrequency ablation (RFA) vs. 2) antiarrhythmic drugs (AADs).

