**Definitions:**

The *diagnosis criteria for PVC-CM* is based on LVEF  $\leq$  45% (by echocardiography) and average PVC burden  $\geq$  10% in an ambulatory ECG Holter monitor that meet the inclusion and exclusion criteria (Table 1), regardless of severity and time of onset. LVEF and PVC burden must be within 150 days of Enrollment Visit (Day 0).

*Responders are defined as an LVEF increase greater than 10% points regardless of intervention.*

If screening confirms eligibility (LVEF  $\leq$ 45% and PVC burden  $\geq$  10%), a baseline visit will be scheduled to obtain subject's demographics and medical history, 12-lead ECG, Minnesota living with HF quality of life (QOL) questionnaire, NYHA functional class and cardiac magnetic resonance (CMR) if clinically indicated. Subjects that refuse enrollment, will be asked to participate in a PVC-CM registry to follow their response and crossover to different treatment strategies.

If subjects meet inclusion criteria (Table 1) during screening, informed consent should be obtained. Stratified randomization to either RFA or AADs will be performed at the time of enrollment (baseline visit, week 0). Based on our preliminary data, we expect that around 30% of subjects will have a PVC burden  $>$ 20%. Thus, a *stratified randomization based PVC burden (assessed by Holter) above and below 20% is needed to assure that subjects in both groups (RFA vs. AAD) are equally distributed between PVC burden above and below 20%.* Stratified randomization will be performed using approved software available at the Coordinating Center only.

If a subject is randomized to the RFA arm, a RFA procedure (Visit 1) should be scheduled at the time of randomization due to usual 8-week next available RFA appointment in most participating centers. Yet both, RFA and AAD interventions should only occur or be initiated after completion of a 3-month observation (Table 2 - Visit Tx-V1, week 12-15).

A 3-month observation period will assess spontaneous variation of PVC burden and improvement or deterioration of LV function. During the final 3-month observation visit (Week 12), LVEF and Holter will be repeated to confirm eligibility if PVC burden and LVEF remains  $\geq$ 10% and  $\leq$ 45%, respectively.

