iii. *Observation – Visit 3.* Similar to Visit 1, appropriate data collection forms should be used to collect current medical therapy, NYHA functional class and Minnesota HF quality of life questionnaire (QOL). 12-lead ECG should be obtained if clinically indicated. Transthoracic echocardiogram should be performed to assess LVEF and a copy mailed to the Echo Core laboratory led by [name] III, M.D. The local PI and designated site staff will be able to log in to iRhythm's ZioReports to obtain the Zio Patch report that should include a 2-week PVC burden.

[figure not shown]
If PVC burden remains  $\geq 10\%$  and LVEF  $\leq 45\%$ , then the subject will either initiate antiarrhythmic drugs or undergo RFA procedure (see Section C: Description of the intervention/treatment) and will continue on protocol as scheduled. However, if these criteria are no longer met, the subject is considered a screen failure and is withdrawn from the study. In such a case, the treatment decision is solely at the discretion of the electrophysiologist caring for subject. Nevertheless, this subject will be included in a PVC-CM registry if consent was provided (described above Section A.1).

i) *Treatment – Visit 1.* This is considered the baseline visit where PVC suppression strategy assignment is initiated (either RFA or AADs). If the subject is randomized to RFA, we will request that sites complete the RFA data collection form which includes information during the RFA procedure as well as recovery, complications and hospital stay. EPS will be performed on their baseline medications, except for antiarrhythmic drugs class II (beta blockers) which will be held at least 5 half-lives prior to procedure. Beta blockers should be resumed after RFA.

iv. However, subjects randomized to AADs can have this visit combined with Observation-Visit 3. In addition, subjects in the antiarrhythmic (AAD group) will require a baseline TSH and LFTs (AST only) if amiodarone is chosen.

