#### **D. Description of the intervention(s)/treatment(s).**

Prior to intervention, all subjects should complete a 3-month observation period consisting of a total of 3 visits. Subjects that are not able to wait or be observed for this period of time should not be considered for this study. Subjects will be randomized to intervention at the baseline visit of observation. Crossover between different treatment arms (RFA vs. AADs) is not encouraged and will not be allowed before 6-month follow-up duration of the treatment period, unless considered critical for the subject's well-being.

ii) Treatment or intervention arms will consist of: Antiarrhythmic drug (AAD) therapy. AAD therapy of choice is amiodarone due to its proven safety in subjects with LV dysfunction. Amiodarone loading dose of 10 grams is recommended, followed by maintenance dose of 200-400mg daily to achieve successful PVC suppression. We define successful PVC suppression only if  $\geq 80\%$  absolute reduction in PVC burden is achieved after a drug or intervention. Alternatively, sotalol and/or propafenone could be considered at the discretion of the electrophysiologist (sotalol dose of at least 120mg twice daily, propafenone 150-300mg tid) if there is a significant concern of safety profile of amiodarone. Finally, other AADs (class Ic) are acceptable if there is a clear preference by the clinical electrophysiologist while a rationale is requested for such choice. Overall, we suggest avoiding class Ia antiarrhythmic drugs due to the prior documented risk of pro-arrhythmia, however, they could be considered in subjects with an implantable or external defibrillator (Lifetest). Optimal heart failure medical therapy should be continued in combination with AAD throughout the 12-month follow-up. Throughout the 12-month follow up period, subjects will have a total of 5 visits to assess changes in clinical status, arrhythmia burden including PVCs and LVEF as outlined in Table 2 and Figure 1. In addition, subjects receiving amiodarone as antiarrhythmic (AAD group) will require a baseline TSH and LFTs and should be repeated every 6 months.

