#### *Rate of responders to PVC suppression*

Besides improvement in LV systolic function, no study has been designed to demonstrate clinical benefits with either RFA or AADs. Clinical benefits are implied based solely on the improvement of LVEF. Based on prior retrospective and observational studies, the rate of responders (improvement of LVEF) to PVC RFA is estimated at 50-65%. Unfortunately, there is no recent data on antiarrhythmics due to the lack of recent studies. Our preliminary data from the CHF-STAT study demonstrates a response rate of 28% (Preliminary Data Section).

We plan to further identify the rate of responders after PVC suppression by obtaining the following primary end-points: 1) improvement in LVEF (determined by  $\Delta \text{LVEF} = \text{final LVEF} - \text{baseline LVEF}$ ) and 2) “responders” to PVC suppression (defined as change in LVEF  $\geq 10\%$ ). In addition, we will obtain QOL and NYHA functional class questionnaires (secondary end-point described above). Each subject will serve as its own control, since all data obtained will be compared between the end of 3-month observation period (control phase - prior to randomization) vs. 3-month after PVC suppression strategy, regardless of treatment randomization (RFA and AAD). We hypothesize that a PVC suppression strategy (RFA or AAD) is better than optimal HF medical therapy alone to improve LV function, HF symptoms, heart failure admissions, and avoid the need for defibrillator. *The PAPS pilot study will help us determine the rate of responders to PVC suppression strategy in order to properly estimate sample size and power the large randomized PAPS study.*

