### **c. Potential Risks**

The study will be conducted according to Good Clinical Practice Guidelines, the Declaration of Helsinki and US 21 CFR. Current clinical practice offers radiofrequency ablation (RFA) plus optimal medical therapy to the population of interest (frequent PVCs associated with cardiomyopathy) supported only on retrospective and non-randomized observational studies with a relatively short (3-6 months) follow up period. Alternative treatments include use of antiarrhythmics and/or optimal medical therapy alone. Risks associated with RFA include cardiac tamponade, bleeding, stroke, AV block, myocardial infarction

and even death. Risks related to antiarrhythmic drugs include common significant drug-to-drug interactions and side effects depending on specific drugs, which commonly leads to poor compliance. Amiodarone for instance, as the primary proposed antiarrhythmic drug in this pilot study, can have significant side effects such as dizziness/lightheadedness, pro-arrhythmic (ventricular tachycardia, torsade de Pointes), thyroid disorders, elevated liver enzymes, optic neuritis, pneumonitis and lung disease depending on dosing. In contrast, optimal medical therapy alone is not considered to add any additional risks to the current illness, however, it is unclear if by not eliminating PVCs (either with RFA or antiarrhythmics) we are potentially withholding a beneficial intervention. Our study proposes to randomize these subjects to two groups: 1) RFA and 2) AAD only after a 3-month observation period (control). The risks of the subjects participating in this research proposal are considered small primarily because most of these subjects would undergo RFA as frequent yet unproven therapy. A 3-month observation period (control) is an ethical intervention since 1) no randomized controlled study has been performed to assess if RFA is better than optimal medical therapy 2) this elective procedure usually is scheduled 8-12 weeks after diagnosis in most high volume medical centers, and 3) it is unclear if PVCs would decrease with time and without intervention with subsequent improvement of LV function without the need for invasive procedures. Finally, our study would not impose any psychological, financial or legal issues.

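### Subjects randomised openly at week 0 can be withdrawn at week 12 or later, so the plan as written does not deliver its stated intention-to-treat comparison, and no analysis set is defined

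*Combined protocol and SAP*

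**What the plan says.** **Allocation.** Section A describes "1:1 random allocation to one of two un-blinded PVC suppression groups". Definitions gives the time: "Stratified randomization to either RFA or AADs will be performed at the time of enrollment (baseline visit, week 0". Section D agrees: "Subjects will be randomized to intervention at the baseline visit of observation". Table 2, Observation Visit 1 in Section B, and the Enrollment, Retention and Follow up Plans say the same.

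**Week-12 check.** Definitions: "During the final 3-month observation visit (Week 12), LVEF and Holter will be repeated to confirm eligibility". For subjects who fail it, Section B, Observation Visit 3, states: "However, if these criteria are no longer met, the subject is considered a screen failure and is withdrawn from the study". The text after Table 1 and the subsection on spontaneous recovery in Section F repeat the withdrawal.

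**Later withdrawals.** The text under Table 2 and item 2 of Section H remove subjects who cross over before 6 months of treatment. Treatment Visit 2 in Section B makes crossover an automatic withdrawal and gives no time limit. The text after Table 2 also withdraws a subject who becomes pregnant on the drug arm.

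**Analysis.** The Project Summary, and Methods under Specific Aims, say: "The treatment regimens will be compared in an intention-to-treat analysis". The text under Table 2 mentions intention-to-treat only for crossover after 6 months. Section I names no analysis population.

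**Other statements on order.** Section F, on responders, refers to the "end of 3-month observation period (control phase - prior to randomization". Potential Risks says the study will "randomize these subjects to two groups: 1) RFA and 2) AAD only after a 3-month observation period (control".

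**The concern.** An intention-to-treat comparison keeps every randomised subject in the assigned arm. Calling someone a screen failure twelve weeks after allocation does not undo the randomisation. If the withdrawal rules are followed, the arms compared at month 12 are not the arms that were randomised.

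Two things are at stake. The first is the RFA versus AAD comparison of LVEF, which is listed as primary. The site knows the arm throughout observation, may titrate medical therapy in that time, and obtains the echo used at week 12. Removal could therefore depend on the arm.

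The second is Aim 1, which concerns feasibility of enrolling, randomising and retaining subjects. The retention rate depends on whether week-12 failures count as randomised, and the plan does not say.

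**Working it through.** **1. Order of events.** Five places put randomisation at week 0: Definitions, Table 2, Observation Visit 1, Section D, and the Enrollment, Retention and Follow up Plans. The responder text in Section F calls the observation period prior to randomisation, which contradicts them. The Potential Risks sentence can be read two ways: randomised only after observation, or treated only after observation. The second reading agrees with week 0.

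**2. Who leaves after randomisation.**
- Subjects failing the week-12 check, before treatment.
- Subjects crossing over before 6 months, after treatment starts.
- Subjects becoming pregnant on the drug arm.

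All three groups go to a registry that needs consent. For early withdrawals the registry relies on chart review. It does not restore the randomised set.

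**3. Which reading decides.** The Table 2 footnote wants the LVEF result available at Observation Visit 3. Table 2 and Section B place the echo at that same visit, with a copy mailed to the core laboratory. Drug-arm subjects may start treatment at that visit. No section says whether the site LVEF or the blinded core-lab LVEF governs, and only the site reading is sure to be available. At Observation Visit 2 the echo is only booked. By the Table 2 windows the two visits are 84 - 63 = 21 to 96 - 51 = 45 days apart. That is booking time, not core-lab turnaround.

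**4. The plan's own allowance.** Sample size justification raises the pilot from 30 to 36-39, citing 15% for spontaneous improvement during observation. A 15% loss leaves 36 × 0.85 = 30.6 to 39 × 0.85 = 33.2 subjects, so the target of 30 is kept.

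**5. Number withdrawn at week 12.** Section F expects fewer than 10%, but words this for LVEF and PVC recovery together. The rate of failing either criterion is not given and cannot be lower than the rate of failing both. Assuming 5-15%:
- lowest: 36 × 0.05 = 1.8
- highest: 39 × 0.15 = 5.9

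That is about 2-6 subjects, or 1-3 per arm if evenly spread.

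**6. Retention denominator (illustration with assumed counts).** Take 39 randomised, 4 week-12 failures and 4 later dropouts, so 39 - 4 - 4 = 31 complete.
- Failures counted as randomised: 31/39 = 79%.
- Failures treated as never enrolled: 31/35 = 89%.

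The ten-point gap comes from the label alone. The safety plan adds to the doubt: it calls 15 subjects half the sample size, which implies 30 rather than 36-39.

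**The case against.** The withdrawal is disclosed, and the pilot was enlarged for it. Week-0 allocation has a stated practical reason: most centres have about an 8-week wait for an ablation slot. The check uses a pre-treatment value and the same rule in both arms. The Zio reading is automated and blinded, and a blinded core-lab echo reading exists. Under the plan's baseline assumption (mean LVEF 25%, SD 5), 45% lies (45 - 25)/5 = 4 SD above the mean, so the LVEF criterion would rarely trigger. The trial is a feasibility pilot, and the Data Sharing Plan says its data are not meant to settle the benefit of either strategy.

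Most of this stands, and it limits the severity. It does not remove the contradiction between the withdrawal rules and the intention-to-treat statements. Entry is allowed up to 45%, so real subjects may sit nearer the threshold, and the PVC criterion operates separately.

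A reader might infer more than the documents support:
- **That the comparison is biased.** This is not shown. Equal loss by arm would be expected to cause little distortion, and nothing in the plan indicates unequal loss.
- **That the sample size is wrong.** The 36-39 already allows for spontaneous improvement. The 140 for the full trial is called preliminary, and Section F already plans to use the pilot's observed rate to power that trial.
- **That Potential Risks flatly contradicts week-0 allocation.** It is ambiguous; only the responder text is a clear slip.

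**Conclusion.** The point holds as an inconsistency between the design and the stated analysis. Followed as written, the plan removes randomised subjects by three routes, states intention-to-treat without exception in two places, and defines no analysis set. The reading that decides the week-12 check is not named.

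About 2-6 of the 36-39 subjects are affected at week 12, assuming 5-15% loss. The documents give no rate for early crossover or pregnancy, so those removals are not counted. Arm-dependent loss is possible because allocation is open, but it is not demonstrated. This should be fixed, at the low end of that grade, because the trial is a feasibility pilot and the remedy is mainly wording.

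**What to change.** Choose one course and state it in the Project Summary, Specific Aims, Section B (Observation Visit 3) and Section I.

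**(A) Intention-to-treat.** Keep all randomised subjects in follow-up and analyse them as randomised. For week-12 failures, count month 12 from the week-12 visit; the existing week-64 visit is 64 - 12 = 52 weeks later. State that the comparison then concerns the assigned strategy and includes subjects who never start suppression, since the primary endpoint is now worded as change after suppression. Cost: 12-month follow-up for about 2-6 subjects at the assumed loss, within limited funds.

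**(B) Modified intention-to-treat.** Keep the week-12 withdrawal and drop the unqualified label. Prespecify the set as randomised subjects who pass the check, decided on the blinded core-lab LVEF and the Zio reading. Reconcile Table 2 with Observation Visits 2 and 3 on echo timing, so that this reading is available before treatment starts. Cost: core-lab turnaround before treatment starts.

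Neither option needs extra subjects or changes how withdrawn subjects are treated. In either case:
- reconcile the early-crossover and pregnancy withdrawals (text after Table 2, Treatment Visit 2, Section H) with the chosen set, so that available outcomes are analysed in the assigned arm;
- report all post-randomisation removals by arm and by criterion;
- count week-12 failures as randomised when reporting retention;
- correct the responder text in Section F and clarify Potential Risks;
- align the and/or wording after Table 1 with Definitions and Section B, where failing either criterion leads to withdrawal.

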### **C. Clinical Assessment and tests**

Regardless of group assignment, all subjects will undergo clinical evaluation and a series of clinically indicated tests and interventions as outlined in Table 2 and Figure 1.

c. 1. 12-lead ECG will be performed at each center and sent to the ECG/Holter core lab (led by [name], UCSF, San Francisco, CA) where a cardiologist blinded to treatment group will provide a final interpretation. Scheduled ECG is requested as noted in Table 2 if clinically indicated. We will assess QRS duration and QT interval of non-PVC beats and PVC features such as location, QRS duration and coupling interval or prematurity.

c. 2. Ambulatory Holter monitor (Zio Patch, iRhythm, Inc). This Holter monitor will be provided directly by iRhythm, Inc. to participating centers. Subjects will mail the device back directly to iRhythm where it will be analyzed and results will be provided to each center. This monitor will provide automatic assessment of daily PVC burden remaining blinded to the group assignment. Custom software designed by [name] will be used to measure PVC coupling interval, coupling interval variability, and number of PVC morphologies. This will allow us to assess important PVC features during the observation period and treatment arms. Reports will be sent to the ECG/Holter core lab (noted above) for final interpretation. Similar to the ECG, the reader will be blinded to the group assignment. The ambulatory Holter monitor will allow us to assess long-term PVC burden and morphology and compare efficacy to achieve successful PVC suppression (defined as PVC reduction  $\geq 80\%$ ) between RFA and AAD groups. Furthermore, it will provide information such as PVC recurrence, and the presence of non-sustained and/or sustained ventricular tachycardia.

c. 3. Transthoracic Echocardiogram. Scheduled 2D-Echocardiograms should be requested as noted on Table 2 if clinically indicated. Echocardiograms will be performed using a commercial system with a 5MHz standard cardiac probe with at least 70-80 frames per second. Echocardiography will be considered adequate if echocardiographic windows allow assessment of the following parameters, otherwise, echo contrast should be performed. LV function will be assessed by quantifying the calculated LVEF (Simpson's formula), fractional shortening (FS), LV end-systolic and diastolic dimensions (LVESD, LVEDD), LV thickness, left atrial (LA) size, mitral valve (MV) function, LV compliance (E/A ratio and E/E' ratio), and dyssynchrony. Interventricular dyssynchrony will be evaluated by RV and LV electromechanical delay (time from onset of QRS to the onset of pulmonary and aortic systolic flow, respectively). LV mechanics / dyssynchrony will be assessed by 1) septal to posterior wall delay, 2) PW-TDI maximum systolic motion delay between septal, anterior, posterior and lateral wall, and 3) 2D

speckle tracking strain analysis (radial, circumferential and longitudinal strain). A copy of the echocardiogram images should be sent to the Echo core laboratory (led by [name], III) for final interpretation by a cardiologist blinded to the randomization arm. Assessment of LVEF by echocardiography will be repeated during observation and treatment phases in order to assess changes in LV function during observation period and between PVC suppression strategies.

c.4. Cardiovascular magnetic resonance (CMR). If clinically indicated, a delayed enhancement CMR will be performed at each center following a single protocol (approved by CMR core laboratory Director: [name], Richmond, VA) and sent to the CMR core lab for final interpretation. Similarly, CMR core lab and participants will remain blinded to group assignment. CMR will be obtained at baseline if clinically indicated to assess LV volumes, mass, ejection fraction, and mid-wall circumferential strain; overall myocardial T1, T2, and extracellular volume fraction (ECV); and scar location and extent using late gadolinium enhanced methods according to previously published techniques. Associations between each CMR assessment and improvement in LV function (responders) will be determined after PVC suppression strategy. Interstitial myocardial fibrosis and outcomes between early- vs. late-coupled PVCs in an attempt to support a mechanistic aim in final PAPS study. The CMR will be considered clinically indicated to exclude other types of cardiomyopathy, and all sites have agreed to order CMR on enrolled subjects.

c.5. Minnesota living with heart failure quality of life (QOL) and NYHA functional class questionnaires to be used in the PAPS study will be approved by [name] (Heart failure core lab). These questionnaires will be provided to each center to be answered by each subject in their local institution. This will allow us to assess heart failure symptoms and change in quality of life and functional status during the observation period and between both treatment groups. Questionnaires will be sent directly to the Heart failure core lab. *All QOL and NYHA questionnaires will be evaluated and graded by an event adjudication committee (independent of the steering committee, see Section G. Ethical / Regulatory Affairs). If clinically indicated, we will request to provide brain natriuretic peptide (BNP) levels as well as CRP and ESR as per schedule on Table 2.* Participants who are evaluated by study staff and suspected to be depressed will be referred to a primary care provider to facilitate the evaluation.

c. 6. Complications, heart failure admissions and adverse events. *All events* including mortality, hospital admissions and heart failure exacerbations and treatment-related complications will be documented on each subject throughout the observation and treatment periods. Each center will report any adverse events to the Coordinating Center (McGuire VA Medical Center, Richmond VA) within 24-48 hours of the occurrence or knowledge of the event. *All SAE/hospital admissions, procedure complications and events will be evaluated and assigned by an event adjudication committee (see Section G. Ethical / Regulatory Affairs and documents: Human subjects and Data Safety Monitoring plan for details).*

*Participating centers will provide all available clinical data to respective core labs (echocardiogram, cardiac MR and Holter) and Coordinating Center (McGuire VA Medical Center) through REDCap with a case number without identifiers and treatment randomization as outlined in the Manual of Operations and Standard Operating Procedures manual.*

Of note, subject participation and results of this study will not change diagnostic testing (e.g. electrophysiologic studies for other indications) and medical management including medical therapy (unless safety drug interactions are clear) and indicated procedures (e.g. left heart catheterization). ICD implantation is not encouraged (but not prohibited) during the study as the CM may improve or even resolve after RFA of PVCs as recently shown by Penela et al..

